13.4 Waiver of elements of informed consent—surgeons

We request a waiver of specific elements of consent regarding medical treatment, medical risks, costs, and injury to surgeon participants. This study does not involve medical treatment of surgeons, and these elements of informed consent would not apply to surgeons participating in this study. We have therefore removed these sections from the model consent form. Omission of this information does not constitute greater than minimal risk and would not adversely affect the surgeon participant.

13.5 Other people present during audiotaped visits

Individuals other than the patient and attending surgeon may be present during the audiotaped clinic visit. This includes family members, residents, nurses and medical students. Although

they are not study participants, they will receive written notification that the visit will be or is currently being recorded. We will allow individuals who do not verbally agree to be audiotaped to step out of the room during the time the audio recorder is on. This approach has been previously used with patients considering high risk operations and it has been tolerated well by their companions and other clinic staff. However, if individuals who do not verbally agree to be audiotaped do not wish to leave the room, we will not audio record the visit, out of sensitivity to the patient's needs.

APPENDIX I: USUAL CARE – PATIENT BASELINE SURVEY

You have been given a booklet to complete for this study. The booklet contains some questions we would like to ask you before you meet with your surgeon.

1. Directions on how to complete each set of questions are written on the top of each set.
2. You will be given the site coordinator's name and telephone number. You can call any time with any concerns or questions.
3. It is very important that you return the booklet to us.
4. Please hand the completed survey to the site coordinator.

Thank you for taking the time to help us.

[figure not shown]
PATIENT BASELINE (T0) SURVEY— USUAL CARE

Research Coordinator: Thank you for agreeing to participate in the study. I just have a few short questions I would like to ask you before you meet with your surgeon. This should take about 5 to 10 minutes to complete. And before we get started with those questions, I just have few things I would like to mention. First, your doctors and nurses know that you are helping us with this research but they will not be able to hear or see your responses to the questions I am going to ask you. Second, this is not a quiz; there is no right or wrong answer, I am just interested hearing your thoughts and feelings. Lastly, if you feel uncomfortable at any time, please let me know. Your participation in this study is voluntary, and you do not have to answer any questions that you do not want to.

Any questions before we start?

Great. Every person is different when it comes to how involved they are in making medical decisions. For example, some people say, “I’d rather have doctors make the decisions about what’s best than for the doctors to give me choices” and some people say “I’d rather be given choices about what’s best for my health than to have the doctor make the decisions for me.”

1. What is your preference for making decisions about your health care?
 - I prefer to make the decision about which treatment I will receive.
 - I prefer to make the final decision about my treatment after seriously considering my doctor’s opinion.
 - I prefer that my doctor and I make the decision together about which treatment is best for me.
 - I prefer that the doctor makes the final decision about treatment that will be used, while seriously considering my opinion.
 - I prefer leaving all decisions about my treatment to my doctors.
2. On a scale from 0 to 10, where 10 means extremely well-informed and 0 means not informed at all, how informed do you feel about surgical options for your breast cancer?

This set of questions includes some reasons other women have given for choosing their breast cancer surgery. We are interested in what is important to you. On a scale from 0 to 10, how important are each of the following to you as you consider different surgery options for your breast cancer?

How important is it to you to...

	Importance Scale										
	Not at all important Extremely Important										
	0	1	2	3	4	5	6	7	8	9	10
3. keep your breast?											
4. remove your entire breast in attempt to gain peace of mind?											
5. avoid having radiation											

6. (*If you currently have a preference to treat your early stage breast cancer*), which treatment do you prefer?

- I am not sure
- Lumpectomy and radiation
- Lumpectomy only
- Mastectomy
- Other surgery

Other Surgery: _____

7. Have you met with your oncologist to discuss treatment options prior to this visit with the surgeon?

- Yes
- No

(*If yes*), who did you meet with?

- Another surgeon
- Medical oncologist
- Radiation oncologist
- Other

(*If other*), specify _____

8. Did you review any information before coming to see your surgeon today?

- Yes
- No

(If yes), what types of information did you review before meeting your surgeon?

(If yes), how much time did you spend reviewing the information?

- Less than 15 minutes
- 15 - 60 minutes
- More than 1 hour

(If no), can you tell me why you did not review any information?

If patient is uncertain, offer categories to see if that prompts a response:

- I saw my surgeon very quickly after my diagnosis
- I didn't look for any
- I was feeling too stressed
- Other _____

9. Did you have any trouble finding information?

- Yes
- No

(If yes), can you tell me what was hard about it?

10. How confident are you filling out medical forms by yourself?

- Not at all
- A little bit
- Somewhat
- Quite a bit
- Extremely

11. How often do you have someone help you read hospital materials?

- Always
- Often
- Sometimes
- Occasionally
- Never

12. How often do you have problems learning about your medical condition because of difficulty understanding written information?

- Always
- Often
- Sometimes
- Occasionally
- Never

13. What is the preferred email address for us to send the follow-up survey?

NOTE: This information will be entered into the Rave electronic data entry system on the Patient Status: Baseline form by coordinator, and used only by a web service to send you the link for the follow-up survey.

14. What is the preferred mailing address for us to send the incentive after you complete the follow-up survey?

NOTE: This information below will NOT be entered into the Rave electronic data entry system.

APPENDIX II: INTERVENTION – PATIENT BASELINE SURVEY

You have been given a booklet to complete for this study. The booklet contains some questions we would like to ask you before you meet with your surgeon.

1. Directions on how to complete each set of questions are written on the top of each set.
2. You will be given the site coordinator's name and telephone number. You can call any time with any concerns or questions.
3. It is very important that you return the booklet to us.
4. Please hand the completed survey to the site coordinator.

Thank you for taking the time to help us.

[figure not shown]
PATIENT BASELINE (T0) SURVEY—INTERVENTION

Research Coordinator: Thank you for agreeing to participate in the study. I just have a few short questions I would like to ask you before you meet with your surgeon. This should take about 5 to 10 minutes to complete. And before we get started with those questions, I just have few things I would like to mention. First, your doctors and nurses know that you are helping us with this research but they will not be able to hear or see your responses to the questions I am going to ask you. Second, this is not a quiz; there is no right or wrong answer, I am just interested hearing your thoughts and feelings. Lastly, if you feel uncomfortable at any time, please let me know. Your participation in this study is voluntary, and you do not have to answer any questions that you do not want to.

Any questions before we start?

Great. Every person is different when it comes to how involved they are in making medical decisions. For example, some people say, “I’d rather have doctors make the decisions about what’s best than for the doctors to give me choices” and some people say “I’d rather be given choices about what’s best for my health than to have the doctor make the decisions for me.”

1. What is your preference for making decisions about your health care?
 - I prefer to make the decision about which treatment I will receive.
 - I prefer to make the final decision about my treatment after seriously considering my doctor’s opinion.
 - I prefer that my doctor and I make the decision together about which treatment is best for me.
 - I prefer that the doctor makes the final decision about treatment that will be used, while seriously considering my opinion.
 - I prefer leaving all decisions about my treatment to my doctors.
2. On a scale from 0 to 10, where 10 means extremely well-informed and 0 means not informed at all, how informed do you feel about surgical options for your breast cancer?

This set of questions includes some reasons other women have given for choosing their breast cancer surgery. We are interested in what is important to you. On a scale from 0 to 10, how important are each of the following to you as you consider different surgery options for your breast cancer?

How important is it to you to . . .

	Not at all important Extremely Important										
3. keep your breast?	0	1	2	3	4	5	6	7	8	9	10
4. remove your entire breast in attempt to gain peace of mind?	0	1	2	3	4	5	6	7	8	9	10
5. avoid having radiation	0	1	2	3	4	5	6	7	8	9	10

6. (*If you currently have a preference to treat your early stage breast cancer*), which treatment do you prefer?

- I am not sure
- Lumpectomy and radiation
- Lumpectomy only
- Mastectomy
- Other surgery

Other surgery: _____

7. Have you met with your oncologist to discuss treatment options prior to this visit with the surgeon?

- Yes
- No

(*If yes*), who did you meet with?

- Another surgeon
- Medical oncologist
- Radiation oncologist
- Other

(*If other*), specify _____

8. Did the clinic offer to send you a website to review before coming to see your surgeon today?

- Yes

No

If you answered "Yes" to question #8, please continue below.

If you answered "No" to question #8, please proceed directly to question #15.

9. Did you agree to have them send the website to you to review?

Yes

No

If you answered "Yes" to question #9, please continue below.

If you answered "No" to question #9, please proceed directly to question #15.

10. Were you able to review the website sent to you before coming to see your surgeon today?

Yes

No

(If yes), how much time did you spend reviewing the website that was sent to you?

Less than 15 minutes

15 - 60 minutes

More than 1 hour

(If no), why did you not review the website?

If patient is uncertain, offer categories to see if that prompts a response:

I saw my surgeon very quickly after receiving website

I didn't have internet access between when I received the website and when I saw my surgeon

I didn't receive the email

I couldn't make the link to the website work

I was feeling too stressed

I didn't think I needed any information

Other _____

11. Did you have any trouble opening or using the website?

Yes

No

(If yes), can you tell me what was hard about it?

12. Did you like getting the website sent to you by email?

Yes

No

(If no), what did you not like about it?

13. On a scale of 0 to 10, where 10 means very helpful and 0 means not at all helpful, how helpful did you find the breast cancer websites that were emailed to you?

Not at all helpful

Very helpful

0 1 2 3 4 5 6 7 8 9 10

14. Would you recommend receiving breast cancer information via email to other patients who are facing the decision for breast cancer surgery?

I would recommend it

I don't have an opinion one way or the other

I would not recommend it

15. How confident are you filling out medical forms by yourself?

Not at all

A little bit

Somewhat

Quite a bit

Extremely

16. How often do you have someone help you read hospital materials?

- Always
- Often
- Sometimes
- Occasionally
- Never

17. How often do you have problems learning about your medical condition because of difficulty understanding written information?

- Always
- Often
- Sometimes
- Occasionally
- Never

18. What is the preferred email address for us to send the follow-up survey?

NOTE: This information will be entered into the Rave electronic data entry system on the Patient Status: Baseline form by coordinator, and used only by a web service to send you the link for the follow-up survey.

19. What is the preferred mailing address for us to send the incentive after you complete the follow-up survey?

NOTE: This information below will NOT be entered into the Rave electronic data entry system.

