7.1.2 Institutional Crossover to Intervention (Decision Aid)

Each site will start in the usual care arm. At the start of each wave, starting from wave two, two sites will crossover into the intervention arm (see Section 4.4 for additional details). Each site will be notified four weeks prior to their crossover date.

After the date of crossover to the intervention, all patients within the clinic will be asked whether they would like to receive the decision aid by email as accepted practice in the clinic. This design, where receipt of the decision aid is not linked to study consent, maximizes reach of the decision aid intervention itself, especially important when working with disadvantaged patient populations that are less likely to participate in research.⁶⁹

Staff will offer the decision aid when a surgery consult is scheduled and maintain a log of all patients who are offered the decision aid. If a patient expresses interest in receiving the decision aid, clinic staff will obtain and record their preferred email address, and they will send the patient the decision aid. Because of privacy concerns, the email body does not include the word “cancer”. The email will be sent by a staff member to an email address supplied by the patient themselves.

Patients who report difficulty with internet access will be offered two options: (1) have the decision aid sent to a family member, and (2) view the decision aid in clinic on an iPad. Although the decision aid is currently only available in English, we will offer it to all patients regardless of primary language, assuming patients may identify ways it could be beneficial (e.g. review with English speaking family member). For patients with visual impairment, the decision aid will be offered using an alternative strategy, such as (but not limited to) emailing it to family members to review.

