If patients decline to participate in the interview, the research coordinator will record age, race, ethnicity, insurance, and reason for declining. These data points will be collected so that we may assess whether participants are categorically different than non-participants. This data is completely de-identified. As these patients have declined research, they will not be approached for future research activities. This decline applies only to that specific research activity and any subsequent research activities. The decline does not apply to any prior data collection unless specified by the patient.

Patients who did accept the decision aid:

Patients will be eligible to participate in **telephone, video, or in-person interviews** addressing Accessibility Barriers if they reported difficulty accessing the decision aid (from baseline survey) or did not use the decision aid (from baseline survey). We will purposefully sample patients who experienced access barriers (identified through survey responses). If we find there is a strong association between accessibility barriers and

socioeconomic disadvantage, or that accessibility barriers cluster within certain clinics, we will oversample based on those factors.

Patients will be eligible to participate in a **telephone, video or in-person interview** addressing Preparatory/Interactional Barriers if they accepted the decision aid. We will focus our sampling on patients with low engagement in decision-making, defined as the lowest tertile for either the PEPPi score or the Street Activation measure. We will purposefully sample patients with low engagement who experienced one or more of the preparatory or interactional barriers outlined in the primary objective (quantitative data collection). We will use other relevant data such as patient age, race, and ADI to ensure a range of participants. We will consider surgeon and clinical site to minimize clustering of interview participants at the provider or site level.

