40. Did the website help you think about the pros and cons of each option?	1	2	3	4	5
41. Did the website help you think about which pros and cons are most important?	1	2	3	4	5
42. Did the website help you know that the decision depends on what matters most to you?	1	2	3	4	5
43. Did the website help you organize your own thoughts about the decision?	1	2	3	4	5
44. Did the website help you think about how involved you want to be in this decision?	1	2	3	4	5
45. Did the website help you identify questions you want to ask your surgeon?	1	2	3	4	5
46. Did the website prepare you to talk to your surgeon about what matters most to you?	1	2	3	4	5
47. Did the website prepare you for a follow-up visit with your surgeon?	1	2	3	4	5

48. Where did you review the website? Check all that apply.

- On my own computer at home
- On a computer at my family or friend's home
- On my own tablet or mobile phone
- On my family or friend's tablet or mobile phone
- On a public computer (ex. library)
- On a iPad in clinic
- Other

(If other), specify _____

49. Did anyone else review the website? (Either with you or you sending them the link)

Yes

No

(If yes), who? Check all that apply.

Partner/spouse

Family member

(If family member), specify _____

Friend

Other

(If other), specify _____

50. Did you have any trouble opening or using the website?

Yes

No

(If yes), what was hard about it?

The following questions are for all patients, regardless of whether they did and did not review the website sent to them from the clinic.

51. Did you like getting the website sent to you by email?

Yes

No

(If no), what did you not like about it?

52. What do you think would be the best format for you to receive and review information from the clinic?

- Paper version
- Computer-based version
- DVD-based version
- Other

(If other), specify _____

53. If the clinic continued to send web-based material prior to the first appointment with the surgeon, what would be the best way to receive this material?

- By email
- By electronic medical record, such as using a patient portal (MyChart)
- By text
- By mail
- Other

(If other), specify _____

Below are some questions so we can learn a little more about you. This information will help us understand how decision making between the surgeon and patient may be differ between patients, and how to better support patients in making their decision about breast cancer surgery.

1. What is the **highest** level of school or degree you have completed?

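### Intervention baseline Q8–Q9 make no provision for the family-member and clinic-iPad routes, so some women may skip the pre-consult use and access items or be asked questions that do not fit

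*Combined protocol and SAP*

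**What the plan says.** Section 7.1.2: after crossover, all patients are asked whether they want the decision aid by email. Those who report difficulty with internet access are offered two options: "have the decision aid sent to a family member, and (2) view the decision aid in clinic on an iPad".

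Appendix II (intervention baseline survey): Q8 asks whether the clinic offered to send the woman a website. Q9 asks "Did you agree to have them send the website to you to review". The routing after a No is "to question #9, please proceed directly to question #15", and a No at Q8 has the same destination. Q10–Q14 lie behind these two gates.

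Section 8.3.2: women who declined, according to the clinic log, may be interviewed about accessibility. Women who accepted qualify if they "reported difficulty accessing the decision aid (from baseline survey) or did not use the decision aid (from baseline survey").

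Section 12.1.1: survey responses on accessibility are summarised, and their association with socioeconomic disadvantage is explored.

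Appendix IV (follow-up, aid accepted): Q48 asks where the website was reviewed and includes the option "On a iPad in clinic" as well as the devices of family or friends.

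**The concern.** The alternative routes exist for women with poor internet access, and Section 1.5.1 treats accessibility barriers to a web-based aid as a critical thing to evaluate. Yet the baseline survey is written as if personal email were the only route. A woman who reads Q9 literally, having seen the aid on the clinic iPad or through a relative's email, may answer No and be routed like a refuser.

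Three uses of the data are at stake:

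- **Description of pre-consult use.** The conceptual model in Section 1.2 turns on review of the aid before the consultation. Q10 is the only item that asks about it directly.
- **Interview selection.** A woman recorded as an acceptor in the log but routed past Q10–Q11 is neither a log decliner nor someone who reported difficulty or non-use at baseline. Under Section 8.3.2 she can fall between the two groups. The Appendix VII guide for acceptors also branches on baseline Q10 and Q11, so she has no defined branch.
- **Association with disadvantage.** Any missing answers would arise among women with internet difficulty, so they may not be missing at random with respect to disadvantage.

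**Working it through.** The plan gives no figure to reproduce. The check is a trace of the routing, followed by a comparison of instruments.

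**1. Routing in Appendix II**

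| Answers | Next items |
|---|---|
| Q8 No | Q15 (Q10–Q14 skipped) |
| Q8 Yes, Q9 No | Q15 (Q10–Q14 skipped) |
| Q8 Yes, Q9 Yes | Q10–Q14, then Q15 |

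A No at either gate costs five numbered items; two Yes answers cost none. Q15–Q17, the health-literacy items that Section 10.1.4.3 lists under accessibility barriers, are asked of everyone.

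**2. Fit of each route in Section 7.1.2**

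- *Email to the woman:* Q8–Q14 all fit.
- *Sent to a family member:* Q8 can be a truthful Yes, because the email offer comes first. Q9 could go either way.
- *Clinic iPad:* Q8 can again be Yes. Read literally, Q9 is No. If she answers Yes, Q10 asks about a site sent to her and reviewed before she came, which does not describe viewing in clinic.
- *Both alternatives:* Q12–Q14 ask about email delivery or emailed material. Q11 (trouble opening or using the site) fits any route, but only if she reaches it.

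**3. What Appendix IV recovers for a woman who skipped Q10–Q14**

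| Baseline item | Follow-up source | Recovered? |
|---|---|---|
| Q10, reviewed before consult | Q34 (after the visit) with Q37 (any time) | Q34 No and Q37 Yes: yes, reviewed before. Both No: not reviewed. Q34 Yes: before cannot be separated from after |
| Q10, time spent before | Q34 time covers post-visit review only | No |
| Q10, reasons for not reviewing | None | No |
| Q11, trouble | Q50 | Only if Q34 or Q37 is Yes, so not for a woman who never got the site open |
| Q12, liked email delivery | Q51 | Yes, but still worded for email |
| Q13 helpfulness rating, Q14 recommendation | Not repeated (Q38–Q47 cover preparation) | No |

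Q48 and Q49 add place of review and who else reviewed it. Limits: Q34 and Q37 keep the wording about a site sent to her; follow-up may not be returned; and the text does not say which booklet an iPad or family-route woman receives. The declined-aid booklet (Appendix V) asks about information in general and has no item on trouble opening the site.

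**4. Size, as illustration only**

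- Section 1.5.1: 36 of 68 pilot decliners cited limited internet comfort or access. Approached: 309 + 68 = 377. 36/377 = 9.5%.
- Assume 40–60% of the 563 patients enrol after crossover: 0.40 × 563 × 36/377 = 22; 0.60 × 563 × 36/377 = 32.
- The 50–62 extension patients, all exposed to the intervention, add 50 × 36/377 = 5 to 62 × 36/377 = 6.

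These figures show how many women might resemble the pilot's internet-related refusers. They do not estimate uptake of the alternative routes or the number of skipped answers.

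**The case against.** The strongest reply is that the skip follows the answer, not the route. Section 8.2.2 prefers oral administration, so a coordinator can clarify Q9. The Appendix VII guide itself uses sent to cover routes other than personal email, which suggests staff may read the word broadly. This stands, and it defeats any inference that the survey sends every iPad or family-route woman past the items. It does not remove the risk: paper completion is allowed, and Appendix II has a coordinator prompt at Q10 but none at Q8 or Q9.

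A reader might also infer that access data for this group are lost. The documents do not support that. Follow-up Q34 with Q37 identifies pre-consult review in many cases, and Q48–Q50 cover place, company and trouble. The clinic log records acceptances, declines and reasons (Section 7.1.4), and vendor access counts are planned per patient (Section 10.1.4.3). The back-up is still partial. The log description does not list the delivery route, and nothing says that a visit through a clinic iPad or a relative's link can be attributed to the patient.

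Two further inferences fail. That accessibility would look too favourable is not shown: women helped on a clinic iPad may have had less trouble than others, so omitting them could overstate difficulty. That the instruments contradict each other because Appendix IV lists the iPad is weak: the same option appears in the usual-care and declined-aid booklets as part of a general list of places.

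Finally, the consequences are bounded. Decline status and reach come from clinic records, the primary analysis is by intention to treat, and the accessibility analysis is largely descriptive. Section 13.1.3 describes interview eligibility through survey responses generally, which could admit follow-up answers. Section 8.3.2, however, names the baseline survey, and the two should be aligned.

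**Conclusion.** The concern holds in a limited form. Baseline Q8–Q9 do not accommodate the two alternative routes in Section 7.1.2, and Q10 and Q12–Q14 are worded for sent or emailed delivery. Some of the women for whom those routes were created may skip the baseline use and access items or be asked questions that do not fit.

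For women who complete the accepted-aid booklet, follow-up recovers part of this. It does not recover pre-consult use in women who also reviewed the site afterwards, pre-consult reasons for not reviewing, or anything for non-responders.

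The number affected is unknown: it depends on uptake of the alternative routes and on how many of those women answer No, neither of which the documents give. The direction of any bias is also unknown. The primary outcomes are unaffected; the effect is confined to the exploratory accessibility analysis and the selection and conduct of interviews.

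**What to change.** For remaining enrolment, reword the baseline items to cover every route in Section 7.1.2:

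- Q8: did the clinic offer you a website about breast cancer surgery, by email to you, to a family member, or on a tablet in clinic?
- Q9: did you accept it in any of these ways?
- Q10: did you look at it, in any of these ways, before meeting your surgeon?
- Q12–Q14: refer to the way she received the website, not to email alone.

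For women already enrolled, add a short derivation rule to Section 12.1.1:

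- Take acceptance from the clinic log, not from Q8–Q9.
- Treat skipped Q10–Q14 in log-acceptors as not asked, never as not used.
- Use follow-up Q34, Q37, Q48 and Q50 to fill use and trouble where possible, and report how many women remain unclassified.
- Amend Section 8.3.2 so that these follow-up answers also qualify women for the accessibility interviews.

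The cost is a revised booklet and script and one analysis rule. Item wording will differ slightly between early and late intervention patients. Rewording reaches only women still to be enrolled: extended recruitment runs at six sites until 12/31/2021 (Section 12.1.3). The derivation rule is therefore what protects the data already collected.
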